4.2. Study 2. Relationship Between Brain Health and CoCoA-PAD Performance

Participants

All participants from Study 1 who live within driving distance of Plymouth ($n=81$) will be invited to undergo a magnetic resonance imaging (MRI) assessment. As such, study 2 will consist of participants who fit into each diagnostic criteria from Study 1.

Sampling

This study will use a convenience sampling procedure based on recruitment to Study 1 and participant location. A cross-sectional design will be employed.

Procedure

Participants will undergo MRI assessment following their participation in Study 1.

Measures

This study will measure the relationship between CoCoA-PAD subtest scores and key indicators of neuronal health. MRI data will be obtained using both single (T1-weighted) and multi-shell imaging approaches.

The specific measures of brain health include:

1. Volumetric measures using T1-weighted imaging of key regions of interest (ROI) associated with early Alzheimer's disease.
2. Diffusion Tensor Imaging (DTI) measures, including Fractional Anisotropy (FA), Radial Diffusivity (RD) and Mean Diffusivity (MD) of defined white matter tracts associated with Alzheimer's disease.
3. Neurite Density Index (NDI), Free Water Fraction (FWF), and Orientation Dispersion Index (ODI) metrics from Neurite Orientation Dispersion and Density Imaging (NODDI) of key grey matter regions of interest.

Figure 3 illustrates the estimated post-diagnostic participant numbers from Study 1.

4.3. Study 3. Measuring the Ability of CoCoA-PAD Subtests at Determining Change Over Time

Participants

A sub-sample of 36 participants from the Study 1 sample will be reassessed on CoCoA-PAD approximately one year after their initial engagement in the CoCoA-PAD study. 18 participants will be selected from both the healthy control and prodromal AD groups.

Sampling

This study will use a criterion based sampling procedure, selecting participants from Study 1 retrospectively based on diagnostic classification.

Procedure

Participants will complete the CoCoA-PAD battery a second time, approximately 11-15 months after their initial assessment.

Measures

The primary outcome measure will be change in scores on CoCoA-PAD subtests (time 2 – time 1 score). This study will therefore use a retrospective (known-group) between-group quasi-experimental research design.

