4.4. Study design summary

A summary of the sample size, sampling approach, and research design for the three sub-studies is outlined in Table 2.

Table 2. Summary of sampling size, sampling approach and research design

Study	Total Sample	Sampling Approach	Design	Primary Outcome Measure
-------	--------------	-------------------	--------	-------------------------

1	120	Stratified: 60 MCI and 60 SCD, matched to population demographics	Prospective between group quasi-experimental research design	CoCoA-PAD index and subtest scores.
2	81	Convenience: based on proximity to Plymouth	Cross sectional research design	CoCoA-PAD subtest scores Diffusion tensor imaging measures (FA, RD and MD) of key white matter tracts Neurite Density Index (NDI) of key grey matter regions of interest.
3	36	Stratified: 18 people with prodromal AD and 18 healthy controls.	Retrospective between group quasi-experimental research design	Change scores on CoCoA-PAD subtests (time 2 – time 1 subtest scores).

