11.3. Sample Size

Given that there are three independent studies, a justification of the proposed sample is outlined for each study.

Study 1: Diagnostic Accuracy of CoCoA-PAD Subtests

The aim of this study is to test whether CoCoA-PAD subtests can distinguish between healthy controls (i.e., people with subjective memory problems without any evidence of AD biomarkers or cognitive decline) and people with preclinical and prodromal Alzheimer's disease. This study uses a prospective research design, and therefore exact participant numbers in each diagnostic criteria cannot be determined until after data collection. Figure 3 provides an estimate of the final sample composition, which includes of 36 healthy controls, 18 people with preclinical AD, and 40 people with prodromal AD. A power calculation using a fixed one-way ANOVA (estimated effect size $f = 0.33$ (moderate effect), $k = 3$) required a minimum sample of 90 to achieve the required power ($\alpha = 0.05$, $1-\beta = 0.8$). Based on current projections (36 controls, 18 preclinical AD, and 40 with prodromal AD), this would be achieved.

Study 2: The relationship between CoCoA-PAD subtests and the health of key brain regions

This study aimed to measure the strength of the association between key brain regions and performance on CoCoA-PAD subtests. It includes a subgroup of study 1 participants. A power calculation using a linear multiple regression (fixed model, single regression coefficient, effect size f^2 (0.1, small) required a minimum sample of 64 participants to achieve the required power ($\alpha = 0.05$, $1-\beta = 0.8$).

Study 3: Testing whether CoCoA-PAD is sensitive to pathological cognitive decline in AD

This study aimed to compare 1 year change score (time 2 score – time 1 score) on CoCoA-PAD subtest scores in people with early Alzheimer’s disease and healthy controls. It includes a subgroup of study 1 participants. A power calculation using a matched pairs *t* test (Cohen’s *d* = 0.5 (moderate)) required a sample of 27 to achieve the required power ($\alpha = 0.05$, $1-\beta = 0.8$).

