11.4. Provisional Data Analysis

The CI will work with a medical statistician, [name], to finalise the data analysis plan, and will publish this on Open Science Framework, prior to the start of data collection. This will ensure both rigour and transparency. A provisional data analysis plan is outlined for each sub-study below. Furthermore, Appendix 2 provides a specific breakdown of the hypotheses and analysis plan for each CoCoA-PAD subtest. This should be considered provisional and may be subject to change prior to the start of the study.

Study 1: Diagnostic Accuracy of CoCoA-PAD Subtests

The aim of this study is to test whether each CoCoA-PAD subtest can distinguish between healthy controls and people with preclinical and prodromal Alzheimer’s disease. This study will use a Welch’s ANOVA to accommodate unequal variances and sample sizes ($k=3$, healthy controls, preclinical AD, and prodromal AD) and Games–Howell post hoc test. A series of receiver operator curves, area under the curves, and optimised sensitivity and specificity values based on Youden index, will be calculated to measure the diagnostic accuracy of each subtest also.

Study 2: The relationship between CoCoA-PAD subtests and the health of key brain regions

Associations between CoCoA-PAD subtest scores and regional brain volume, density and connectivity will first be explored using Spearman correlations, adjusted for false discovery rate using the Benjamini-Hochberg Procedure. Multiple linear regression models will then be used to assess the predictive value of MRI-derived volumetric measures on CoCoA-PAD performance, adjusting for potential confounders including age, sex, education, and intracranial volume. Model fit and assumptions will be evaluated to ensure robustness.

Study 3: Testing whether CoCoA-PAD is sensitive to pathological cognitive decline in AD

Change scores on CoCoA-PAD subtests will be calculated by subtracting time 1 score from time 2 score. As such, negative change scores will denote a decline in performance. A series of *t* tests will be used to test whether the prodromal AD group exhibit higher levels of cognitive decline over a one-year interval. To control for the false discovery rate (FDR) across multiple *t*-tests, the Benjamini–Hochberg procedure was applied with a threshold of $q = 0.05$. This method adjusts *p*-values to reduce the risk of Type I error when conducting multiple comparisons.

Data Analysis Software

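### Study 3 is sized for a matched-pairs t test, but the planned analysis compares two unmatched groups of 18, where power at d = 0.5 is about 31% (two-sided) to 43% (one-sided), not 80%

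*Protocol*

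**What the plan says.** Section 11.3 sets the aim of Study 3 as comparing one-year change on "CoCoA-PAD subtest scores in people with early Alzheimer’s disease and healthy controls". The same paragraph then takes a matched-pairs t test with a moderate effect (d = 0.5), alpha 0.05 and power 0.8, and reports that this "required a sample of 27 to achieve the required power". It does not say whether the test is one-sided or two-sided, or what d standardises.

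The design and analysis sections describe a comparison between groups:

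- Section 4.3, participants: "18 participants will be selected from both the healthy control and prodromal AD groups", 36 in total.
- Section 4.3, measures: the outcome is the time 2 minus time 1 score, and "This study will therefore use a retrospective (known-group) between-group quasi-experimental research design".
- Section 4.4, Table 2: "Retrospective between group quasi-experimental research design".
- Section 11.4: a series of t tests on change scores "will be used to test whether the prodromal AD group exhibit higher levels of cognitive decline over a one-year interval", with Benjamini-Hochberg control at q = 0.05.

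No section describes pairing individual patients with individual controls.

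**The concern.** The pairing within a person is used up when time 1 is subtracted from time 2. What remains is one change score per person in two separate sets of people, so the test is an independent-samples t test. At the same d and the same total number of people, that test has much less power than a paired one, and the 27 does not describe it.

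Study 3 provides the longitudinal data for primary objective iv in Section 3.1, sensitivity to deterioration over a year. Section 7.8 says that insensitive tests will be dropped from the battery depending on the results. If power is well below the stated 80%, a subtest that does track decline could be judged insensitive only because 18 per group were too few to show it.

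**Working it through.** **Inputs.** d = 0.5, alpha = 0.05, target power 0.80 and N = 27 (Section 11.3); 18 per group (Section 4.3 and Table 2). Assumption: for the between-group test, d is the mean difference in change divided by the SD of change. All powers use the noncentral t distribution.

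**Step 1. Reproduce the 27.** For a paired test, df = n − 1 and the noncentrality is d√n.

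- One-sided, n = 27: 0.5 × √27 = 2.598, df = 26, critical t = 1.706, power 81.2%. At n = 26 the power is 79.8%, so 27 is the smallest n that reaches 80%.
- Two-sided, n = 27: critical t = 2.056, power 70.6%. Reaching 80% needs n = 34 (power 80.8%).

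The stated 27 is therefore a correct result for a one-sided paired test. That sidedness is inferred from the match; the protocol does not state it.

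**Step 2. The planned test.** For independent groups, df = n₁ + n₂ − 2 and the noncentrality is d√[n₁n₂/(n₁ + n₂)]. With 18 and 18, √(324/36) = 3, so the noncentrality is 0.5 × 3 = 1.5 with df = 34.

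| Test, 18 v 18, d = 0.5 | Critical t | Power | d for 80% power | n per group for 80% at d = 0.5 |
|---|---|---|---|---|
| Two-sided 5% | 2.032 | 30.8% | about 0.96 | 64 |
| One-sided 5% | 1.691 | 43.1% | about 0.85 | 51 |

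**Step 3. Does any paired reading recover 80%?** Suppose the 36 participants formed 18 true patient-control pairs with d = 0.5 on the within-pair difference. The noncentrality is 0.5 × √18 = 2.121 with df = 17, and power is 65.2% one-sided or 51.6% two-sided. Needing 27 pairs would mean 54 people. If the paired test instead meant change within one group, each group has 18, again fewer than 27, and the group comparison would not be tested at all.

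**Step 4. Multiplicity.** A Benjamini-Hochberg adjusted p-value is never smaller than the raw one, so power for any one subtest can only fall from the values in Step 2. The size of the fall depends on how many subtests truly differ and how they correlate. The protocol gives neither, so no figure is offered.

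**The case against.** Several points on the other side are fair.

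- **Sidedness.** Section 11.4 words the hypothesis directionally, and 27 itself implies a one-sided test. A reader might take 80% against 31% as the cost of using the wrong test. It is not like for like: on the one-sided basis that yields 27, the planned test has 43%. The range of 31% to 43% is the accurate statement.
- **Meaning of d.** In a paired calculation, d is the mean difference over the SD of the differences. If 0.5 was meant as within-person change, the between-group value could be larger or smaller. The powers above therefore rest on a stated assumption.
- **The 36.** A reader might infer that the protocol presents 36 as a margin over 27. The Study 3 paragraph makes no such comparison; the remark that the required number would be achieved belongs to Study 1.
- **Study 3 as a whole.** A reader might infer that Study 3 is expected to find nothing. Power below 50% makes a non-significant result more likely than not for a given subtest at d = 0.5. It does not follow that every subtest will be non-significant.
- **Provisional analysis.** Section 11.4 is provisional and is to be finalised with a statistician. That could change the multiplicity family, but a comparison of change between 18 and 18 by t test has these powers whatever the family.

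None of this restores 80%, and the mismatch between the sizing test and the planned test stands.

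**Conclusion.** The concern holds as a mismatch between the test used for sizing and the test planned. The arithmetic behind 27 is sound for a one-sided paired test, but Study 3 does not plan that test. For 18 v 18, power is about 31% two-sided or 43% one-sided at d = 0.5, before false discovery rate control and with no allowance for loss to follow-up. The design reaches 80% power only for a between-group difference in change of about 0.96 SD (two-sided) or 0.85 SD (one-sided), well above the moderate effect named. These figures assume alpha 0.05, equal groups of 18 and d defined as the between-group difference in change over its SD.

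A reader might go further and conclude that Study 3 must be reclassified as estimation or its set of tested subtests cut down. Those are design choices; correcting the error requires neither.

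**What to change.** Replace the Study 3 paragraph in Section 11.3 with an independent-groups calculation that states the sidedness and defines d as the between-group difference in change divided by its SD. Suggested wording: *With 18 participants per group and a two-sided 5% test, power is 31% for d = 0.5 and reaches 80% only for d of about 0.96, before false discovery rate correction.* If a one-sided test is intended, say so and give 43% and about 0.85 instead.

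In Section 11.4, add that the between-group difference in change will be reported with a 95% CI for each subtest, and that a non-significant result alone will not be treated as evidence that a subtest is insensitive to change.

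The cost is a change of wording and a less favourable stated power. No extra participants are needed.

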11.4. Provisional Data Analysis

The CI will work with a medical statistician, [name], to finalise the data analysis plan, and will publish this on Open Science Framework, prior to the start of data collection. This will ensure both rigour and transparency. A provisional data analysis plan is outlined for each sub-study below. Furthermore, Appendix 2 provides a specific breakdown of the hypotheses and analysis plan for each CoCoA-PAD subtest. This should be considered provisional and may be subject to change prior to the start of the study.

Study 1: Diagnostic Accuracy of CoCoA-PAD Subtests

The aim of this study is to test whether each CoCoA-PAD subtest can distinguish between healthy controls and people with preclinical and prodromal Alzheimer’s disease. This study will use a Welch’s ANOVA to accommodate unequal variances and sample sizes ($k=3$, healthy controls, preclinical AD, and prodromal AD) and Games–Howell post hoc test. A series of receiver operator curves, area under the curves, and optimised sensitivity and specificity values based on Youden index, will be calculated to measure the diagnostic accuracy of each subtest also.

Study 2: The relationship between CoCoA-PAD subtests and the health of key brain regions

Associations between CoCoA-PAD subtest scores and regional brain volume, density and connectivity will first be explored using Spearman correlations, adjusted for false discovery rate using the Benjamini-Hochberg Procedure. Multiple linear regression models will then be used to assess the predictive value of MRI-derived volumetric measures on CoCoA-PAD performance, adjusting for potential confounders including age, sex, education, and intracranial volume. Model fit and assumptions will be evaluated to ensure robustness.

Study 3: Testing whether CoCoA-PAD is sensitive to pathological cognitive decline in AD

Change scores on CoCoA-PAD subtests will be calculated by subtracting time 1 score from time 2 score. As such, negative change scores will denote a decline in performance. A series of *t* tests will be used to test whether the prodromal AD group exhibit higher levels of cognitive decline over a one-year interval. To control for the false discovery rate (FDR) across multiple *t*-tests, the Benjamini–Hochberg procedure was applied with a threshold of $q = 0.05$. This method adjusts *p*-values to reduce the risk of Type I error when conducting multiple comparisons.

Data Analysis Software

Data analysis will be conducted using SPSS, Jamovi, and RStudio.

12. Dissemination of Results

The study findings will be disseminated through a range of tailored strategies to ensure accessibility and impact across key audiences. Results will be shared with research participants via a co-produced, accessible information infogram, developed in collaboration with the study's PPI group to ensure clarity and relevance. A second, professionally targeted infogram will also be co-developed with the project's professional co-production team to communicate the findings to memory service professionals and researchers. Both infograms will be made available on the CoCoA-PAD website, which is hosted by University of Plymouth.

Academic dissemination will include submission of research articles to peer-reviewed journals, as well as practitioner-facing journals and professional magazines. Study findings will also be presented at academic and clinical conferences, including a planned co-presentation with a representative of the PPI group. This presentation will highlight the co-production process and the evaluation of the cognitive assessment tool. In addition, the anonymised dataset and study protocol will be made available via open science repositories to support research transparency and secondary analysis. These dissemination activities will ensure that results reach service users, professionals, and the broader research community in meaningful and accessible formats.

13. Patient and Public Involvement and Coproduction

Patient and Public Involvement (PPI) has been embedded throughout the CoCoA-PAD study design and development. The PPI group comprises five older adults, including two individuals with neurological conditions, one with a background of educational deprivation, and one from an ethnic minority background. The remaining participants have personal experience of dementia, i.e., spouse, siblings or parents. Their perspectives have helped shape a more inclusive and equitable research process. Over the course of the study, seven structured PPI meetings are scheduled. Each meeting is recorded and documented, with formal minutes produced to ensure a transparent audit trail of decisions and input. This record will be used to demonstrate how PPI contributions have been incorporated into the study, and a GRIPP2 checklist will be published alongside all resulting research outputs.

The PPI group has been actively involved in co-producing the full suite of cognitive tasks used in the study. Their input included reviewing early drafts, simplifying instructions, recommending length adjustments to reduce participant fatigue, and advising on how to make the technology interface more accessible for older adults. In addition to shaping the assessments themselves, the group reviewed and approved all participant-facing documents, including the standard and accessible versions of the Participant Information Sheet, Electronic Consent Form, Debrief Form, and Disclosure Materials. Their guidance ensured that all materials were sensitive, clear, and suitable for a diverse ageing population.

The PPI group will also contribute to dissemination by co-producing summary infographics to communicate findings to both participants and professionals. Their ongoing involvement is

central to the ethos of the study, ensuring that it remains grounded in the needs, experiences, and preferences of older adults.

14. List of documents

- 344617 CoCoA-PAD Study Poster. V1. 06.08.2025
- 344617 Participant information sheet. V1. 06.08.2025
- 344617 Accessible participant information sheet. V1. 06.08.2025
- 344617 Electronic Consent form. V1. 06.08.2025
- 344617 CoCoA-PAD Mental Capacity Assessment. V1. 06.08.2025
- BRIC MRI safety adults questionnaire - research participants
- 344617 Study Debrief. V1. 06.08.2025
- 344617 Adverse Event Checklist. V1. 06.08.2025
- 344617 Cognitive Status Disclosure (MCI) V1. 06.08.2025
- 344617 Cognitive Status Disclosure (normal limits) V2. 06.08.2025
- 344617 MRI Disclosure. V1. 06.08.2025
- BRIC_MRI_Local_Rules-12.09.21
- BRIC_Safety_and_Risk_Operational_Policy-12.09.21
- [name] Short Academic CV 06.08.2025
- [name] GCP Refresher 25.03.2024
- OID
- SoECAT

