4.1. Study 1. Evaluating the Diagnostic Accuracy of CoCoA-PAD subtests

Participants

A total of 120 participants will be recruited: 60 participants with subjective cognitive decline (SCD) and 60 participants with mild cognitive impairment (MCI). Participants will be classified post-recruitment into four distinct diagnostic groups: healthy controls, preclinical AD, prodromal AD, and non-AD related MCI. Figure 3 provides a flow of the estimated frequencies of each diagnostic group within the sample.

Sampling

This study will use a stratified sampling approach with post-hoc diagnostic classification. A prospective quasi-experimental between-group research design will be employed.

A stratified sampling approach will ensure that key demographic information, including years of education and ethnicity, will match national population demographics of the UK. 2021 census data revealed that 6% of 70–74-year-olds in the UK are from non-white ethnic minority backgrounds. However, given that people from minority ethnic backgrounds are significantly more likely to have dementia but less likely to receive a diagnosis (Okeoghene Ighomereho, 2025), for the purpose of this study, the stratified sampling target will be inflated to 10%.

Similarly, 2021 census data has mapped the educational attainment of the UK population. No age-specific education attainment values were published, but regional values have been published, and Plymouth demographics have been selected for this study. This is based on coastal communities having higher rates of dementia, lower rates of diagnosis, and significant social inequalities which often exclude them from research (Alzheimer’s Research UK, 2024). This study will replicate educational attainment values, with provision for 5% variation in the recruitment to each education level – see Table 1.

Table 1. Educational Attainment and Stratified Sampling Target

Educational Attainment	Plymouth Demographics	CoCoA-PAD Recruitment Target Range
No Qualification	17%	14-26
Level 1 (O level any grade)	10%	6-18
Level 2 (O levels passes)	14%	11-23
Apprenticeship	6%	1-13
Level 3 (A level equivalent)	17%	14-26
Level 4 (3 rd level qualifications)	34%	35-47
Other	2%	0-8

Procedure

Participants will be recruited and classified post-recruitment into diagnostic groups on the basis of AD biomarker results (pTau-217) and performance on the M-ACE, using a cut-off score of 20 for MCI (Potts et al., 2022).

Measures

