strategies to support cognitive wellbeing. All feedback will be delivered in a sensitive, person-centred manner, and with a written feedback summary. Participants will be provided with information about the referral route for a memory assessment, should they wish to undergo a clinically assessment with a memory service.

This feedback will be primarily provided by the Chief Investigator, a qualified clinical neuropsychologist with substantial experience in cognitive assessment and communicating results to patients and their families. For sites outside of the primary research centre, feedback will either be delivered directly by the Chief Investigator or by a local research nurses trained and supervised by the Chief Investigator.

This approach reflects ethical guidance that supports sharing clinically meaningful information with participants when it is generated using validated tools, has clear interpretive value, and can support health literacy and informed decision-making.

CoCoA-PAD Disclosure

The study also includes novel digital cognitive assessments developed under the CoCoA-PAD protocol. These assessments are research tools under development and currently lack an any normative data or diagnostic benchmarks to interpret results in individual participants. Without reference values or validated clinical thresholds, it is not possible to determine what constitutes 'normal' or 'impaired' performance in the older adult population. Therefore, results from these digital cognitive tasks will not be disclosed to participants, as doing so would be speculative.

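### Study 1 plans only unadjusted group tests and raw ROC curves, so its contrasts and AUCs may mix AD effects with age, sex and education effects; adjusted estimates should be added beside them

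*Protocol*

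**What the plan says.** Protocol section 11.4 (Study 1): the group comparison is a Welch's "ANOVA to accommodate unequal variances and sample sizes", with three groups (healthy controls, preclinical AD, prodromal AD) and Games–Howell post hoc tests. It adds "A series of receiver operator curves, area under the curves, and optimised sensitivity and specificity values based on Youden index" for each subtest. No covariate is named for Study 1 there or in Appendix 2.

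Section 11.4 (Study 2): the regressions of CoCoA-PAD performance on MRI volumes are planned "adjusting for potential confounders including age, sex, education, and intracranial volume".

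Section 4.1 (Procedure): participants are classified after recruitment by pTau-217 and "performance on the M-ACE, using a cut-off score of 20 for MCI". No age or education adjustment of that score is stated.

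Section 7.7: the CoCoA-PAD tests "currently lack an any normative data or diagnostic benchmarks to interpret results in individual participants". Subtest scores therefore cannot be norm-corrected before analysis.

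Section 5.5, Table 3: at entry by the PROTECT route, SCD and MCI are separated by performance against demographically adjusted norms. The telephone MoCA route uses a fixed score.

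**The concern.** Objectives (i) and (ii) ask whether the subtests detect AD. A raw contrast answers that only if the groups are alike in other determinants of test score, or if those determinants are modelled. Study 1 does neither. Welch's ANOVA and Games–Howell have no place for covariates, and the ROC curves use raw scores.

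The protocol itself gives reason to expect a link. Section 11.4 treats age, sex and education as possible confounders of these same scores in Study 2, and section 4.6 describes low educational attainment as a risk factor for AD. Section 2.1 criticises existing tests for adding nothing beyond demographic and genetic information in preclinical AD. An unadjusted AUC cannot show that CoCoA-PAD does better than that.

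The results will drive decisions. Section 7.8 says insensitive subtests will be dropped, and section 7.9 makes further development conditional on diagnostic accuracy. A subtest could be kept because it follows age or schooling.

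**Working it through.** **1. The plan's own figure.** Section 11.3 gives a minimum of 90 for a one-way ANOVA with f = 0.33, k = 3, α = 0.05 and power 0.80. With noncentrality λ = f²N and degrees of freedom 2 and N − 3, f = 1/3 needs exactly N = 90, and f = 0.33 gives power 0.793 at 90 and 0.811 at the projected 94 (36 + 18 + 40). The figure reproduces within rounding. No sample-size error is involved.

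**2. Does the design balance the groups?** Table 1's targets refer to the whole sample: 17% of 120 is 20.4, and ±5% of 120 is ±6, which gives the stated 14–26. Tables 2 and 3 also attach demographic matching to the SCD and MCI strata. The analysed groups are formed later, from pTau-217 and M-ACE, and no target applies to them. Age and sex are not stratified at all.

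**3. Where could imbalance enter?**
- Prodromal v control: through the raw M-ACE cut-off, if M-ACE falls with age or lower education. Demographically adjusted entry on the PROTECT route offsets part of this.
- Preclinical v control: both groups are cognitively unimpaired and are split by pTau-217. Confounding arises only if demographics differ by biomarker status.

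**4. Size for a subtest with no AD signal.** The documents give neither an age gap nor an age slope, so both are assumed: a gap of 3–5 years and a score 0.03–0.05 SD lower per year.
- Spurious d = gap × slope: 3 × 0.03 = 0.09 to 5 × 0.05 = 0.25.
- AUC = Φ(d/√2): 0.525 to 0.570.
- Rejection rate, 40 v 36, with noncentrality d/√(1/40 + 1/36) = 4.353d, so 0.39 to 1.09:

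| Test | d = 0 | d = 0.09 | d = 0.25 |
|---|---|---|---|
| Two-sample t, 5% | 5.0% | 6.7% | 18.9% |
| Approximate Tukey critical value, 3 groups | 1.9% | 2.9% | 10.2% |

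The Tukey row is closer to the planned Games–Howell test, but it assumes equal variances. Neither row includes the FDR correction promised in section 4.6.

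**5. Size when there is a real signal.** Let ρ be the within-group score–age correlation and D the standardised age difference (both assumed). The unadjusted AUC is Φ[(δ + ρD)/√2], where δ = √2·√(1 − ρ²)·Φ⁻¹(AUC at a given age). For ρ = 0.2–0.4 and D = 0.2–0.8:
- a true 0.70 appears as 0.704–0.760;
- a true 0.80 appears as 0.796–0.841.

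With D = 0, a true 0.75 appears as 0.746 (ρ = 0.2) down to 0.732 (ρ = 0.4), so the error then runs downward.

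**6. Power after adjustment.** With three covariates, λ = f²N/(1 − R²) and error degrees of freedom N − 6. At N = 94 and f = 0.33, power is 0.811 if the covariates explain nothing, and 0.852, 0.893 and 0.930 if they explain 10%, 20% and 30% of within-group variance. This uses total N only, ignoring the unequal group sizes and any group–covariate correlation, which would reduce the gain.

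**The case against.** The strongest reply has four parts.

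*The plan is provisional.* Section 11.4 says so, and a statistician is to finalise and publish it. Covariate sets are often left to that document. This limits how firmly one can say that adjustment will be absent. It does not remove the point, because the protocol names methods that cannot take covariates, so adding them means adding an analysis.

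*Raw ROC and Youden values are a legitimate target.* They describe how a raw cut-off performs in the people sampled. This stands, and is why they should be kept.

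*Entry on the main recruitment route is demographically adjusted.* Section 5.3 aims to recruit everyone through PROTECT. This stands as a partial offset for prodromal v control, but final classification still uses the single M-ACE score.

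*Study 2 asks a different question and begins with Spearman correlations that carry no demographic covariates.* This also stands. A reader might infer a formal contradiction between Studies 1 and 2. The text supports only an inconsistency in how the same scores are treated.

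A reader might also infer that the AUCs will be inflated, or that the raw M-ACE cut-off biases both primary contrasts. The documents support neither: no imbalance or slope is given, balanced groups push the pooled AUC slightly down, and the M-ACE mechanism does not separate preclinical AD from controls.

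**Conclusion.** The point holds as a gap in a stated method that should be closed. Study 1 contrasts and AUCs may carry demographic effects, and the planned analyses cannot show whether they do. The risk is clearest for prodromal v control and conditional on biomarker-related demographic differences for preclinical v control.

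Under the assumed age gap and slope the effect is modest. The false-positive rate of about 3–10% on the Tukey approximation is the more relevant figure; the 7–19% from a plain t-test overstates what the planned procedure would do. Imbalance in education could add to this or offset it. The documents do not support calling the Study 1 results invalid or the direction of bias known.

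**What to change.** In the final analysis plan, for each subtest:

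- Pre-specify a linear model of score on diagnostic group plus age, sex and education, with HC3 standard errors to retain the protection against unequal variances, and test the Appendix 2 contrasts within it.
- Report a covariate-adjusted AUC beside the planned raw AUC and Youden values, which stay.
- Tabulate age, sex and education by final diagnostic group, so that readers can see how much imbalance there was.

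Cost: about 3–4 degrees of freedom out of about 94 participants (3 with education in years, 4 with three attainment bands) and a little analysis work. No extra data are needed, since section 6.2 already collects age, gender and educational history. Section 4.6 keeps biomarker status unknown until Study 1 and 2 data are complete, and the section 8.10 timeline sends plasma in May 2027, so the change can be fixed before group labels exist.
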